### 13.1.2 NHS-IL12

The actual dose for NHS-IL12 is calculated as actual dose administered/weight (µg /kg). The last available weight of the participant on or prior to the day of dosing will be used.

The duration of NHS-IL12 treatment (in weeks) during the study for a participant is defined as:

$$\text{Treatment duration (weeks)} = (\text{last dose date} - \text{first dose date} + 28) / 7$$

The cumulative dose (µg /kg) of NHS-IL12 per participant in a time period is the sum of the actual dose levels that the participant received within that period (i.e., total dose administered (µg) / weight (kg)).

NHS-IL12 will be administered at Day1 of each cycle. The dose intensity (DI) and the relative dose intensity (RDI) will be calculated for each participant across all cycles. The dose intensity per cycle (µg /kg/cycle) is defined as

$$\text{DI (µg /kg/cycle)} = \text{Cumulative dose (µg /kg)} / [\text{treatment duration (in weeks)} / 4]$$

The relative RDI is defined as the actual dose intensity divided by the planned dose per cycle and expressed in %.

$$\text{RDI (\%)} = 100 \times [\text{DI } (\mu\text{g/kg/cycle}) / (\text{planned dose}) (\mu\text{g/kg/cycle})]$$

The summary of treatment exposure and compliance for NHS-IL12 will include the following information:

- Treatment duration (weeks)
- Total number of infusions received
- Cumulative dose ( $\mu\text{g/kg}$ )
- Dose intensity ( $\mu\text{g/kg/cycle}$ )
- Relative dose intensity (%)
  - <50%
  - [50%, 65%[
  - [65%, 80%[
  - [80%, 100%]
  - > 100%

## 13.2 Dose Reductions

Dose reductions of avelumab or NHS-IL12 is defined as actual non-zero dose < 90% of the planned dose.

Number and percentage of participants with at least one dose reduction as well as a breakdown of dose reductions (1 / 2 / 3 /  $\geq 4$ ) will be summarized by cohort.

## 13.3 Dose Delays

Delays will be derived based on study drug administration date and will be grouped into the following categories based on the deviation of the actual to the planned treatment administration day (relative to the previous treatment administration date):

- No delay (including 1 day delay)
- 2-6 days delay
- 7 or more days delay

Number and percentage of participants with delayed study drug administration and maximum length of delay, i.e. the worst case of delay if participants have multiple dose delays will be summarized by cohort.

### **13.4 Infusion rate reductions**

Infusion rate reductions of avelumab as recorded on the eCRF will be used for analysis. Number and percentage of participant with at least one infusion rate reduction as well as a breakdown of infusion rate reductions (1 / 2 /  $\geq 3$ ) will be summarized by cohort.

### **13.5 Dose Interruptions**

Drug interruptions of avelumab or NHS-IL12 as recorded on the eCRF will be used for analysis.

The number and percentage of participants with dose interruptions and the corresponding reasons will be summarized by cohort.

## 14

## Efficacy Analyses

The subsections in this section include specifications for analyzing clinical study endpoints for efficacy as specified in the Clinical Study Protocol to meet the study objectives.

Efficacy analysis will be summarized on the FAS overall, by study cohort and by treatment group (only for UC cohort Stage 2). Additionally, for UC cohort the results will be displayed by combination therapy (Stage 1 + Stage 2 combination therapy group).

### 14.1

### Primary Endpoint: confirmed BOR

The primary efficacy endpoint is the confirmed BOR by Investigator assessment according to RECIST v1.1 by selected tumor type.

Confirmed Best Overall Response will be evaluated according to RECIST v1.1 based on the Investigator's assessment of disease at different evaluation time points from the first study administration date until documented disease progression, according to the following rule.

- Complete response = at least two determinations of CR at least 4 weeks apart and before progression. Namely, second determination date of CR – progression date  $\geq$  at least 4 weeks or at least two determinations of CR without any progression determination.
- Partial response = at least two determinations of PR or better at least 4 weeks apart and before progression (and not qualifying for a CR). Namely, second PR or better determination date – progression date  $\geq$  at least 4 weeks or at least two PR or better determinations without any progression determination.
- Stable disease = at least one SD assessment (or better)  $\geq$  6 weeks after the first study treatment administration and before progression (and not qualifying for CR or PR)
- Non-CR/non-PD (for the participants with non-measurable disease at baseline) = at least one Non-CR/non-PD assessment (or better)  $\geq$  6 weeks after the first study treatment administration and before progression (and not qualifying for CR or PR)
- Progressive Disease = PD  $\leq$  16 weeks after the first study treatment administration (and not qualifying for CR, PR, SD, or non-CR/non-PD).
- Not Evaluable (NE): all other cases.

SD can follow PR only in the rare case that tumor increases by less than 20% from the nadir, but enough that a previously documented 30% decrease from baseline no longer holds. If this occurs the sequence PR-SD-PR is considered a confirmed PR. A sequence of PR – SD – SD – PD would be a best response of SD if the minimum duration for SD definition has been met.

**Objective Response (OR)** is defined as a confirmed BOR of complete response (CR) or partial response (PR) according to RECIST v1.1.

Only tumor assessments performed on or before the start of any further anti-cancer therapy (Drug therapy, surgery and radiotherapy other than radiation with palliative intent) will be considered in the assessment of BOR. Clinical deterioration will not be considered as documented disease

progression. Palliative radiotherapy delivered in a normal organ-sparing technique [within 2 weeks before the start of study treatment or within pretreatment period], erythropoietin, darbepoetin- $\alpha$ , and granulocyte colony-stimulating factor are considered anti-cancer therapy.

The frequency (number and percentage) of participants with confirmed responses (defined as confirmed CR or confirmed PR) will be summarized by study cohort. The ORR will be determined as the proportion of participants with a confirmed BOR of PR or CR. Participants with BOR of NE will be summarized by reason for having NE status. The following reasons will be used:

- No baseline assessments
- No post-baseline assessments
- All post-baseline assessments have overall response NE
- New anticancer therapy started before first post-baseline assessment
- SD of insufficient duration (<6 weeks after Treatment day 1 without further evaluable tumor assessment)
- PD too late (Tumor assessment detecting the PD >12 weeks after Treatment day 1 with no tumor assessment in between)
- Special and rare cases where BOR is NE due to both early SD and late PD will be classified as 'SD of insufficient duration'

Percent change from baseline in sum of longest diameters will be plotted.

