- d. Day 1 of each cycle, EOT Visits, and Safety Visit should include a full physical examination. All other visits should have a focused physical examination with attention paid to immune-related AEs. Eye signs and symptoms should be checked at each visit. If there are clinically relevant findings then an appropriate ophthalmology examination should be obtained within 2 days.
- e. Weight measured at each visit for dose calculation (see Section 6.2.1 for details). Vital signs (blood pressure, pulse, respiratory rate, temperature, oxygen saturation) should be assessed predose (within 15 minutes [ $\pm$  5 minutes] of injection and/or infusion), and then every 15 minutes ( $\pm$  5 minutes) from the start of avelumab infusion for at least 2 hours. See Section 7.4.4.1 for additional details on vital signs collection.
- f. Tumor evaluations during Screening must be performed within 28 days prior to Cycle 1, Day 1 in order to document the baseline status of the tumor disease using RECIST v1.1 target and non-target lesions. Brain CT/MRI scan (either, with contrast preferred) is required at Screening if not performed within the previous 6 weeks. Thereafter, brain imaging should be done only if clinically indicated. A bone scan should be done for clinically indicated tumors at Screening. Bone metastasis detected at Screening need to be followed at subsequent tumor evaluation visits.
- g. Radiographic tumor evaluations have a time window of up to 5 days prior to Day 1 drug dosing and should be performed every 8 weeks while on treatment for the first 6 months (ie, at the end of Cycles 2, 4, 6) and then every 12 weeks thereafter while on treatment. Timing of imaging is independent from treatment delays. Subjects without progressive disease and who are not receiving subsequent anticancer therapy after the EOT Visit will be followed every 8 weeks with radiographic disease evaluation for the first 6 months and then every 12 weeks thereafter, until progressive disease according to RECIST v1.1.
- h. Concomitant medications and procedures will be documented at each study visit until the 50-day Safety Follow-Up visit.

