### 8.5.2.3 Part A: Dose Escalation and Part B: Expansion Cohorts Confirmed Best Overall Response per RECIST 1.1

Best Overall Response will be evaluated according to RECIST v1.1 ([Eisenhauer 2009](#)) based on the Investigator's assessment of disease at different evaluation time points from the first study administration date until documented disease progression, according to the following rules:

- CR = at least two determinations of CR at least 4 weeks apart and before progression
- PR = at least two determinations of PR or better at least 4 weeks apart and before progression (and not qualifying for a CR)
- SD = at least one SD assessment (or better)  $\geq$  6 weeks after the first study treatment administration and before progression (and not qualifying for CR or PR).

---

- PD = progression  $\leq$  12 weeks after the first study treatment administration (and not qualifying for CR, PR, or SD).

Only tumor assessments performed before the start of any further anticancer treatment will be considered in the assessment of BOR. Clinical deterioration will not be considered as documented disease progression.

Objective Response (OR) is defined as CR or PR according to RECIST v1.1 as described above. Subjects who do not have an on-treatment radiographic tumor assessment due to early progression, who receive antitumor treatments other than the study treatments prior to reaching a CR or PR, or who die, progress, or drop out for any reason prior to reaching a CR or PR will be counted as non-responders in the assessment of OR.

For the expansion cohorts, the primary analysis of the BOR will be conducted in the FAS, defined as all treated subjects who had measurable disease at baseline according to Investigator assessment. The number and proportion of confirmed responses (defined as confirmed CR or confirmed PR) will be tabulated. The ORR will be determined as the proportion of subjects with a confirmed BOR of PR or CR.

The analysis of the BOR for the dose-escalation (secondary endpoint) will be conducted in the Full Analysis Set. The ORR, defined as the proportion of subjects with BOR of PR or CR will be tabulated by dose level and overall. The 2-sided 95% Clopper-Pearson CI will be constructed.

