#### 16.3.4.2 Duration of Response

Duration of response is defined, for subjects with confirmed OR, as the time in months from first documentation of OR to the date of first documentation of PD as per RECIST v1.1 or death due to any cause. If a subject has not had an event (PD or death), DOR is censored. The censoring rules for DOR are the same as described below for PFS.

DOR will be summarized for the FAS of subjects with a confirmed OR using the Kaplan-Meier method. The median event time and 2-sided 95% CI for the median will be provided. If the number of subjects with a confirmed CR or PR is small, the data will only be listed.

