### 3 Modification History

Unique Identifier for Version	Date of IAP Version	Author	Changes from the Previous Version
1.0	21OCT2019	PPD	Not Applicable
2.0	20OCT2020	PPD	

Further to the futility analysis, it has been decided to stop the study earlier. Hence, the sensitivity, subgroup and exploratory analyses of the efficacy criteria as well as the analysis of patient reported outcomes were removed.

Section 8.2: updated the categorizations for PD-L1 expression level at Baseline.

Section 11.1: added item ethnicity (Japanese, Non-Japanese).

Section 10.1: added a description for the overview of the impact of COVID-19 events.

Section 10.2.1: added an analysis of COVID-19 related protocol deviations.

Section 15.1.1: added a listing of COVID-19 related events.

Minor corrections in Section 16.2.

Appendix 18.3: table updated (added previously omitted parameter).

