#### **14.4 Secondary Endpoint: Duration of response**

Duration of response is defined, for participants with confirmed OR, as the time in months from first documentation of OR to the date of first documentation of PD as per RECIST v1.1 or death due to any cause. If a participant has not had an event (PD or death), DOR is censored. The censoring rules for DOR are the same as described below for PFS.

DOR will be summarized for the FAS of participants with a confirmed OR using the Kaplan-Meier method. The median event time and 2-sided 95% CI for the median will be provided. If the number of participants with a confirmed CR or PR is small, the data will only be listed.

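### Both analysis plans restate the CR and PR confirmation rule as a date formula that no responder with later documented progression can meet

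*SAP*

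**What the plan says.** Protocol 8.5.2.3 requires, for a confirmed PR, "at least two determinations of PR or better at least 4 weeks apart and before progression". The CR rule has the same form.

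Two plans implement this: the SAP for the dose-escalation part (16.2.3.1) and the IAP for the expansion cohorts (14.1). Both open the CR and PR definitions with the protocol rule. Both then add an explanatory sentence:

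- For CR: "Namely, second determination date of CR – progression date" of at least 4 weeks, or two CR determinations with no progression recorded.
- For PR: "Namely, second PR or better determination date – progression date" of at least 4 weeks, or two determinations of PR or better with no progression recorded.

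The next definition in the list begins "Stable disease = at least one SD assessment (or better") at 6 weeks or later and before progression.

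Duration of response in IAP 14.4 is defined "for participants with confirmed OR, as the time in months from first documentation of OR to the date of first documentation of PD" or death. SAP 16.3.4.2 uses the same definition.

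**The concern.** The lead sentence tests the gap between the two response scans. The formula tests the gap between the second response scan and progression, with the later date subtracted from the earlier one. A responder who progresses after confirmation therefore fails the first branch, and the second branch is closed to anyone with documented PD.

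Confirmed BOR is the primary efficacy endpoint of the expansion cohorts and a secondary endpoint in Part A. If the formula is what was programmed:

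- ORR would fall as follow-up lengthens, because each later progression removes a response already confirmed.
- The loss would be hard to see. The dropped responder has an assessment better than SD at 6 weeks or later, so is reported as SD, not as missing or not evaluable.
- DOR could contain no PD events, only deaths close enough to the last assessment to count under IAP Table 2 (within 8 weeks, or 12 weeks beyond month 6).

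The final analysis runs after the end of study (IAP 6), when responders have had the most time to progress.

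**Working it through.** The visible text gives no target response rate or power for this endpoint, so there is no stated figure to reproduce. The check is date logic plus simple proportions.

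**Inputs**

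- Confirmation rule: protocol 8.5.2.3, repeated in SAP 16.2.3.1 and IAP 14.1.
- Imaging: protocol Table 6, footnote g. Scans "should be performed every 8 weeks while on treatment for the first 6 months", at the end of Cycles 2, 4 and 6, then every 12 weeks. This gives weeks 8, 16, 24, 36, 48, 60, 72.
- UC Stage 1 n = 16 (IAP 6.1). Other planned cohort sizes are 30 (CRC, RCC) and 40 (NSCLC), from protocol 5.1.
- The dash between dates means subtraction elsewhere in both plans: see the treatment-day and duration definitions in SAP 11.5 and 11.7 and IAP 9.

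**One example: PR at week 8, PR at week 16, PD at week 24**

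- Lead sentence: second − first = 16 − 8 = 8 weeks = 56 days ≥ 28, and week 16 precedes week 24. Confirmed.
- Formula: second − PD = 16 − 24 = −8 weeks = −56 days, which is not ≥ 28. PD exists, so the other branch is closed. Not confirmed.

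**All scheduled sequences to week 72**

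Choosing first response, second response and PD in order from 7 scans gives C(7,3) = 35 sequences.

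- Lead sentence: 35 of 35 confirmed.
- Formula: 0 of 35. Second − PD runs from −56 days (for example 16 and 24) to −392 days (16 and 72).

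Extending the grid to week 96 (9 scans) gives C(9,3) = 84 sequences: 84 of 84 against 0 of 84.

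**The no-progression branch**

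This branch leaves out the 4-week spacing. Responses at weeks 8 and 10 without PD fail the lead sentence and pass the formula. Scheduled scans are at least 8 weeks apart, so this matters only for unscheduled scans.

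**Effect on ORR under literal programming**

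Loss per responder with later PD = 100/n: 100/16 = 6.25 points, 100/30 = 3.3 points, 100/40 = 2.5 points.

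The documents do not give the share of responders who progress, so the full range is shown. The 3 true responders out of 16 are an assumption; for r true responders of whom k progress, reported ORR is (r − k)/16.

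| Responders who progress | Reported | ORR | 95% Clopper-Pearson CI |
|---|---|---|---|
| 0 | 3/16 | 18.8% | 4.0–45.6 |
| 1 | 2/16 | 12.5% | 1.6–38.3 |
| 2 | 1/16 | 6.3% | 0.2–30.2 |
| 3 | 0/16 | 0% | 0–20.6 |

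**Effect on the Stage 1 criterion**

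IAP 6.1 opens Stage 2 on 3 or more responders of 16 by confirmed BOR. With an assumed true ORR of 30%, the probability of meeting this is 0.901. If an assumed 10% or 25% of responders have PD documented by the cut-off and are dropped, the effective rate is 27% or 22.5% and the probability falls to 0.848 or 0.733.

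**The case against.** The best defence is that this is a drafting slip with no doubt about intent. The protocol rule is clear, the lead sentences repeat it, and IAP 7 says the protocol's statistical methods were adopted. The worked sequences in IAP 14.1 turn on whether a second PR exists, and DOR makes sense only if PD can follow a confirmed response. A program that produced no PD events in DOR would probably be noticed. All of this supports the lead sentence as the intended rule. None of it removes the formula, which is offered as the meaning of the rule and is the only date arithmetic in the definition. The worked sequences do not cover PR–PR–PD.

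Three narrower points:

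- **Transposed dates.** If PD minus second response was meant, all scheduled sequences pass (84 of 84) and the effect on scheduled imaging is nil. This is a plausible origin for the error. It still tests the wrong interval: responses at weeks 8 and 12 with PD at an unscheduled week-14 scan meet the protocol rule and fail the transposed formula.
- **PD after new anti-cancer therapy.** Such a PD is not considered for BOR, so that responder could pass through the no-progression branch. This stands, but it is not a progression for BOR, and scheduled scanning stops once new therapy starts.
- **Response after PD.** PR, PD, PR would give a positive difference. The opening of the definition limits assessments to those up to documented progression, so this sequence is excluded.

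It is also fair that the planned sizes of 30 and 40 may not have been reached, since the IAP records: "Further to the futility analysis, it has been decided to stop the study earlier".

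**Conclusion.** The concern holds. In both plans, for both CR and PR, the formula contradicts the rule it claims to explain, and no responder with later PD that counts for BOR can satisfy it. The rule as written is wrong for the primary efficacy endpoint of the expansion cohorts.

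The size depends on what was programmed, which the documents do not show. If the lead sentence was used, there is no effect. If the formula was used literally, every confirmed responder who later progresses is lost. The response counts and progression shares used above are assumptions; the actual Stage 1 count is not given.

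The futility decision has already been taken, and nothing here shows it was wrong. The remaining exposure is the final ORR and DOR.

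**What to change.** Delete the two explanatory sentences in IAP 14.1 and the two in SAP 16.2.3.1; the lead sentences are sufficient. If a formula is wanted, use:

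- second determination date − first determination date ≥ 28 days (two CRs for CR; two determinations of PR or better for PR);
- both dates before the first documented PD, if there is one;
- the plans' existing cut-off at further anti-cancer therapy kept as it is;
- no minimum interval from confirmation to PD.

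Then check that the BOR program applies this rule, including the version used for the futility analysis, and report the outcome of that check. The cost is two deleted sentences in each plan and one program check. No new data are needed.

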### 5.3.2 Exclusion Criteria

Subjects are not eligible for this study if they fulfill any of the following criteria (applicable to all subjects, including all expansion cohorts, unless noted otherwise):

1. Concurrent treatment with a nonpermitted drug/intervention (listed below)
  - a. Anticancer treatment (eg, cytoreductive therapy, radiotherapy, immune therapy, cytokine therapy, monoclonal antibody, targeted small molecule therapy) or any investigational drug

within 4 weeks or 5 half-lives, whichever is shorter, prior to start of study treatment, or not recovered from AE related to such therapies, with the following exceptions:

- i. Palliative radiotherapy delivered in a normal organ-sparing technique is permitted (concurrently or within pretreatment period as described in Section 6.5.3)
- ii. Erythropoietin, darbepoetin- $\alpha$ , and granulocyte colony-stimulating factor are permitted
- iii. Hormonal therapies acting on the hypothalamic-pituitary-gonadal axis are permitted (ie, luteinizing hormone-releasing hormone agonist/antagonists). No other hormonal anticancer therapy is permitted
- b. Major surgery (as deemed by Investigator) for any reason (except diagnostic biopsy), within 4 weeks prior to start of study treatment, or not fully recovered from surgery within 4 weeks prior to start of study treatment
- c. Subjects receiving immunosuppressive agents (such as steroids) for any reason should be tapered off these drugs before start of study treatment, with the following exceptions:
  - i. Subjects with adrenal insufficiency, may continue corticosteroids at physiologic replacement dose, equivalent to  $\leq$  10 mg prednisone daily
  - ii. Administration of steroids through a route known to result in a minimal systemic exposure (topical, intranasal, intra-ocular, or inhalation) is permitted
  - iii. Previous or ongoing administration of systemic steroids for the management of an acute allergic phenomenon is acceptable as long as it is anticipated that the administration of steroids will be completed in 14 days, or that the dose after 14 days will be equivalent to  $\leq$  10 mg prednisone daily

2. Any prior treatment with any form of IL-12
3. For the NSCLC, CRC, and UC expansion cohorts, prior therapy with any antibody / drug targeting T-cell co-regulatory proteins (immune checkpoints) such as anti-PD-1, anti-PD-L1, or anticytotoxic T lymphocyte antigen-4 (CTLA-4) antibody is prohibited

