### **6.5.2 Prohibited Medicines**

As mentioned in the exclusion criteria in Section 5.3.2, subjects must not have had any anticancer treatment (eg, cytoreductive therapy, radiotherapy, immune therapy, cytokine therapy, monoclonal antibody, and targeted small molecule therapy with the following exceptions: palliative radiotherapy delivered in a normal organ-sparing technique [within 2 weeks before the start of study treatment or within pretreatment period], erythropoietin, darbepoetin- $\alpha$ , and granulocyte colony-stimulating factor, which are permitted), major surgery, or received another investigational agent within 4 weeks or 5 half-lives, whichever is shorter, before the start of study treatment.

The following treatments must not be administered during the study:

- Immunotherapy, immunosuppressive drugs (that is, chemotherapy or systemic corticosteroids except for short-term treatment of allergic reactions or for the treatment of immune-related adverse events [irAEs]), or other experimental pharmaceutical products.

- Short-term administration of systemic steroid (that is, for allergic reactions or the management of irAEs) is allowed. Steroids with no or minimal systemic effect (topical, inhalation) are allowed.
- Administration of a live vaccine within 30 days prior to study entry.
- Growth factors (granulocyte macrophage colony stimulating factor). Exception: Erythropoietin, darbepoetin- $\alpha$ , and granulocyte colony-stimulating factor are permitted may be prescribed at the Investigator's discretion.
- Herbal remedies with immunostimulating properties (eg, mistletoe extract) or known to potentially interfere with major organ function (eg, hypericin).

Any additional concomitant therapy that becomes necessary during the study and any change to concomitant drugs must be recorded in the corresponding section of the eCRF, noting the name, dose, duration, and indication of each drug.

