## 8.5.2 Analysis of Primary Endpoints

### 8.5.2.1 Part A: Dose Escalation Adverse Events

Adverse events will be coded according to Medical Dictionary for Regulatory Activities. Severity of AEs will be graded using the NCI-CTCAE v4.03 toxicity grading scale.

The incidence of TEAEs regardless of attribution and AEs defined as related to the study treatment will be summarized by Preferred Term and System Organ Class, and described in terms of intensity and relationship to avelumab and M9241. Adverse events (serious and non-serious) will be considered TEAEs when emerging in the on-treatment period defined as the time from the first study drug administration to the last drug administration date + 30 days or the earliest date of subsequent anticancer drug therapy minus 1 day, whichever occurs first, unless otherwise stated.

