### **Definition of on-treatment period**

On-treatment period is defined as the time from the first dose of study treatment through minimum (30 days + last dose of study treatment, start day of new anti-cancer drug therapy – 1 day).

The date of new anti-cancer therapy after treatment start is collected in eCRF pages “Anti-Cancer Treatment after Discontinuation Details” and “Radiotherapy After Discontinuation Details”. Palliative radiotherapy delivered in a normal organ-sparing technique [within 2 weeks before the start of study treatment or within pretreatment period], erythropoietin, darbepoetin- $\alpha$ , and granulocyte colony-stimulating factor are considered anti-cancer therapy.

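### The expansion-cohort analysis plan classes erythropoietin, darbepoetin-alpha and G-CSF as anti-cancer therapy, an undeclared rule that would shift BOR, PFS/DOR and TEAE cut-offs if applied

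*SAP*

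**What the plan says.** **IAP (expansion cohorts).** The sentence appears twice: in Section 9, under the definition of the on-treatment period, and in Section 14.1, on the primary endpoint. In both places a list of pretreatment palliative radiotherapy, erythropoietin, darbepoetin-alpha and G-CSF ends "and granulocyte colony-stimulating factor are considered anti-cancer therapy".

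The term drives three sets of rules:
- Section 14.1 lets scans count towards BOR only up to the start of further anti-cancer therapy.
- Section 14.2 and Table 2 censor PFS at the last evaluable scan before new anti-cancer therapy. Section 14.4 applies the same rule to DOR.
- Section 9 ends the on-treatment period at the earlier of 30 days after last dose and the day before the "start day of new anti-cancer drug therapy". Section 15.1 defines TEAEs by that period.

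On the date source, Section 9 says "The date of new anti-cancer therapy after treatment start is collected in eCRF pages" and names two: the drug-treatment and radiotherapy pages completed after discontinuation.

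**Protocol.** Section 5.3.2, exclusion 1.a.ii, says of the same agents "and granulocyte colony-stimulating factor are permitted". Section 6.5.2 allows them on study at the investigator's discretion ("granulocyte colony-stimulating factor are permitted may be prescribed"). The visible analysis rules do not mention them. Section 8.5.2.1, under a Part A heading, ends the TEAE window at "the earliest date of subsequent anticancer drug therapy minus 1 day" if that comes before 30 days after last dose. Section 8.5.2.3 says "Only tumor assessments performed before the start of any further anticancer treatment will be considered in the assessment of BOR".

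**The concern.** Drugs that the protocol treats as permitted supportive care are classed in the IAP as anti-cancer therapy. The sentence sits beside the rules for both Part B primary endpoints, confirmed BOR and TEAEs, and the same term governs PFS and DOR censoring.

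If a program followed it, a response confirmed after a growth factor would be lost, a progression or death would become a censored time, and adverse events soon after the last dose would leave the TEAE tables. None of this would reflect a change in cancer treatment. IAP Section 7 reports that the protocol's methods were adopted, so a reader of the study report would not know that the classification differs.

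**Working it through.** The documents state no figure for this rule, so there is nothing to reproduce. The check compares the texts and then works out the effect per participant.

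**1. Origin of the sentence.** The IAP list repeats protocol Section 6.5.2 down to its bracket on radiotherapy: "delivered in a normal organ-sparing technique [within 2 weeks before the start of study treatment or within pretreatment period". In the protocol the list ends in permission; in the IAP it ends in classification. Those protocol sections concern eligibility and concomitant use and do not define an analysis term.

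**2. Is the rule stated elsewhere?**
- Protocol 8.5.2.1 and 8.5.2.3: no.
- Part A SAP 11.6 and 16.2.3.1, which have matching cut-offs: no.
- IAP Section 7, where departures from the protocol belong: no.

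This covers visible text only. Protocol 8.5.1 and most of the Part A PFS/DOR table are redacted.

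**3. Which uses would trigger it?** Section 9 takes the date from after-discontinuation pages. IAP Section 12.2 records concomitant drugs on a different page. Under the named source, a growth factor given during treatment therefore triggers nothing. Sections 14.1 and 14.2 name no source of their own.

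**4. TEAE window under the named source.** Let L be the last dose day and L + d the first day of the agent.
- Without the agent, the window ends on L + 30.
- With it, the window ends on min(L + 30, L + d - 1).
- Loss = (L + 30) - (L + d - 1) = 31 - d days for d = 1 to 30, and 0 from d = 31.

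| d | Days lost |
|---|---|
| 1 | 30 |
| 10 | 21 |
| 15 | 16 |
| 30 | 1 |
| 31 or more | 0 |

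**5. PFS and DOR under the named source.** Scans continue off treatment every 8 weeks for the first 6 months and every 12 weeks after that (protocol Table 6, footnote g). IAP Section 9 uses 30.4375 days per month.
- *Progression* at the m-th scan after the agent, with none missed: the event becomes a censored time 8m weeks earlier on the 8-week schedule. For m = 1, 56/30.4375 = 1.84 months; for m = 2, 112/30.4375 = 3.68 months. On the 12-week schedule, m = 1 gives 84/30.4375 = 2.76 months.
- *Death* needs no off-treatment scan. Table 2 counts a death as an event if it falls within 8 weeks of the last scan, or within 12 weeks when that scan is more than 6 months after first dose. If the agent falls between that scan and the death, the event becomes a censored time up to 56 days (1.84 months) or 84 days (2.76 months) earlier.

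**6. BOR under the named source.** BOR changes only when a needed scan follows the agent. A PR at 6 weeks or later whose confirming scan comes after the agent becomes SD. If the agent precedes the first post-baseline scan, BOR becomes NE. Both count as non-response.

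**The case against.** The strongest reply is that this is an editing slip with no demonstrated consequence. The copied list makes a dropped **not** plausible, although the documents do not settle it. No growth-factor usage rate is given. Supportive drugs on treatment go to the concomitant-medication page, and the therapy types tabulated after discontinuation (IAP 12.3) have no growth-factor category beyond Other. All tests are exploratory (IAP 9), SAEs outside the window stay listed with a flag (15.2.2), irAEs are identified up to 90 days after last dose (18.4), and OS does not use the rule. All of this stands and limits the stakes. It does not make the sentence right: the plan still governs tables meant for the study report, submissions and manuscripts.

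Four stronger readings are tempting, and the documents do not support them:
- *That G-CSF during dosing ends the TEAE window or discards scans.* The only named date source excludes this.
- *That the radiotherapy item contradicts the palliative exemption in Section 14.1.* The item is bracketed to the pretreatment period, so it cannot be further or new therapy after first dose. It is awkward but changes no derivation.
- *That the rule was added after the decision to stop early.* The modification history lists only changes between versions 1.0 and 2.0. The sentence may already have been in 1.0, so its absence there shows nothing.
- *That the protocol certainly lacks the rule.* Only its visible text can be checked.

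**Conclusion.** The sentence is wrong as written, or at best an undeclared departure from the visible protocol, and it should be corrected. If applied with the named date source, its effect per participant is:
- 1 to 30 days lost from the TEAE window when the agent starts within 30 days of last dose;
- a progression or death turned into an earlier censored time when it follows a post-discontinuation agent;
- a lost response only where a needed scan follows the agent.

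The total effect is unknown and may be nil. A reader might infer that the Stage 1 urothelial futility count or another reported result was altered; nothing in the documents shows this.

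The sizes assume that the after-discontinuation pages supply the date for every derivation. Section 9 implies this, but Sections 14.1 and 14.2 do not say so. The progression figures also assume that no scheduled scan is missed.

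**What to change.** 1. In IAP Section 9 and Section 14.1, state that erythropoietin, darbepoetin-alpha and G-CSF are **not** anti-cancer therapy for BOR, for PFS/DOR censoring or for the on-treatment period. If the opposite is intended, declare and justify it in Section 7.
2. State that the date source in Section 9 also governs the BOR and PFS/DOR derivations. Section 14.1 counts surgery as well, so the after-discontinuation surgery page listed in Section 12.3 should be named for BOR.
3. Check the programmed exclusion list against the corrected text.
4. As tidying only, delete the pretreatment palliative-radiotherapy item from both sentences.

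The cost is two text corrections, a sentence on the date source and one program check.
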